4 STUDY DESIGN

4.1 OVERALL DESIGN

This is a prospective, open label, single-center, single-arm, pilot diagnostic accuracy study to evaluate the tissue distribution of 68Ga-PSMA Positron Emission Tomography (PET)/CT in 80 patients with high risk localized prostate cancer or biochemical recurrence.

At screening: participants will sign an approved informed consent, medical history and vital signs will be completed. Labs will be drawn for PSA. Eligibility criteria will be verified and completed.

Day of the injection:

Subjects will receive a single IV dose of 3-7 mCi of 68Ga-PSMA (study drug) followed by PET/CT imaging 60-90 minutes after injection. Scan time will be determined based on the capacity of the PET scanner. Scanning will start from the mid-thighs (to minimize radiotracer artifact from accumulation in the bladder) to the base of the skull. There may be exceptions based on clinical relevance that the scan coverage may be extended.

All patients will be closely monitored with vital signs, to be assessed before and after injection of 68Ga-PSMA-11 (Blood Pressure, Heart Rate). Patients will be monitored with respect to vital signs and adverse events during, and 2-hours following radiotracer administration for adverse events.

Post injection:

Patients will receive a phone call 2 days following PET/CT to assess for adverse events that may have developed in a delayed fashion. If there are any concerning study-related adverse events, this will be escalated to clinical evaluation by the study primary investigators.

To minimize bias, all PET/CT images will be interpreted by a board certified radiologist with experience in reading such modalities. They will be blinded to the final outcome, such as the histopathology of any biopsies and the outcome of subsequent imaging.

68-Ga-PSMA PET/CT positivity or negativity will be interpreted, stratified by different anatomic regions as previously defined [1].

REGION DESCRIPTION

1	Prostate and Prostate Bed
2	Pelvis, excluding prostate bed, but including lymph nodes
3	Extra-pelvic soft tissue, including lymph node involvement and metastasis to other organs
4	Bone Metastasis

The presence of prostate cancer (positive or negative) will be reported within these regions.

A. Lymph nodes - considered positive if the 68Ga-PSMA-11 uptake is localized/focal and is greater than the adjacent or mediastinal blood pool. The location of the lymph nodes will be recorded according to one of 7 sub-categories as previously defined[1]:

1	Right Hypogastric/Internal-iliac
2	Left Hypogastric/Internal-iliac
3	Right Obturator
4	Left Obturator
5	Right External-iliac
6	Left External-iliac
7	Other

B. Visceral lesions – These will be considered positive if the 68Ga-PSMA-11 uptake is focal and greater than the physiologic background activity in the organ of interest.

C. Bone lesions – These will be considered positive if the 68Ga-PSMA-11 uptake is focal and greater than physiologic background activity in normal bone marrow.

D. Prostate bed – These will be considered positive if the 68Ga-PSMA-11 activity is focal and greater than the physiologic, background activity in the prostate bed.

Validation of positive 68Ga-PSMA-11 will be based on a combination of histopathology from biopsy or surgical specimens, and follow up imaging. Definition of

true positivity and false negative based on imaging follow previously published methodology[1].

Surgery (prostatectomy) will take place between 7-3 and 14 days after the 68Ga-PSMA 11 injection.

If patients with BR show metastasis, attending urologist will evaluate for surgery, radiation or chemotherapy.

Follow up in clinic will occur at 2 and 6 months after study drug injection. (Visits 3 and 4)

In patients with biochemical recurrence, will repeat the PSMA scan within 1 year, after they completed treatment and when their PSA still increases when initial PSMA was negative, at PI's discretion if needed.

See Appendix 1. Schedule of Events table

4.2 SCIENTIFIC RATIONALE FOR STUDY DESIGN

This is an exploratory, single arm, open label pilot study evaluation of 68Ga-PSMA Positron Emission Tomography with intraprostatic and/or pelvic lymph node uptake determination by PET/CT imaging, with histological confirmation of disease localized and staging. Methodical evaluation of 68Ga-PSMA intraprostatic and or pelvic lymph node will provide important preliminary data upon which further clinical studies can be based.

4.3 JUSTIFICATION FOR DOSE

68Ga-PSMA-11 will be used as the radiopharmaceutical agent for PET imaging at a dose of 3-7 mCi given intravenously. Dosimetry data are available from published data and will reference the Weil Cornell IND application to the FDA.

In summary, the published literature and safety studies in humans indicates no observed adverse events to the radiopharmaceutical[1,7,16]. Measured dosimetry showed that the critical organs affected are, in descending order, the spleen, stomach wall, pancreas and bladder. The reported effective dose of 68Ga-PSMA-11 is 0.0129 mSv/MBq, which is the lowest of the 68Ga based tracers, including those used in imaging of neuro-endocrine tumours such as DOTA-TOC, DOTA-NOC, DOTA-TATE[17–19].

68Ga-PSMA can only be administered via intravenous infusion. The proposed dose (3-7 mCi) is based upon joint guidelines from the European Association of Nuclear Medicine and The Society of Nuclear Medicine and Molecular Imaging, who recommend a dose of 0.049-0.06 mCi/kg. In an average 75kg adult patient, this would be approximately 3.7-4.5 mCi [20].

The 68-Ga-PSMA agent will be manufactured using previously reported procedures using a generator. Agent release criteria, and validation standards for each batch produced will be followed.

4.4 END OF STUDY DEFINITION

A participant is considered to have completed the study if he has completed all phases of the study including the last visit or the last scheduled procedure shown in the Schedule of Activities (SoA), Section 1.3.

Patients who do not complete surgery would be considered Early Termination (pre-surgery).

The investigator may withdraw a subject from the trial for any of the following reasons:

1. Protocol violation,
2. Serious or intolerable adverse event (that in the opinion of the Investigator, requires the subject's discontinuation),
3. The Investigator withdraws the subject (at the Investigator's discretion for reasons other than an adverse event),
4. The Principal Investigator terminates the study,
5. The subject requests to be discontinued from the study, or
6. The subject is lost to follow-up.

5 STUDY POPULATION

5.1 INCLUSION CRITERIA

- 1) Male aged 21 years or older
- 2) Ability to understand and provide written informed consent
- 3) All patients must have histopathological proven adenocarcinoma of the prostate
- 4) ECOG performance status 0-1
- 5) No evidence of other malignancy (except squamous or basal cell skin cancers)
- 6) Consent to use acceptable form of birth control following the imaging period (condoms for a period of seven days after injection if sexually active)

7) a) inclusion criteria specific for the pre-prostatectomy group:
Untreated prostate Cancer with high-risk features, as defined as having at least one of the following criteria:

- i. PSA \geq 20.0 ng/mL
- ii. ISUP Gleason Grade Group 3, 4 or 5
- iii. Clinical stage T3

b) inclusion criteria specific for biochemical recurrence:

- (i) Histopathological proven prostate adenocarcinoma
- (ii) Rising PSA after definitive therapy with prostatectomy or radiation (therapy (external beam or brachytherapy)).

1. Post radical prostatectomy (RP), PSA greater than or equal to 0.2 ng/ml measured more than 6 weeks after RP.
2. Post-radiation therapy, PSA that is equal to or greater than 2 ng/ml rise above PSA nadir

5.2 EXCLUSION CRITERIA

- 1) Unable to tolerate a PET/CT (e.g. unable to lie flat)

- 2) Recent history of a secondary malignancy in the past year, excluding non-melanoma skin cancer (non-metastatic)
- 3) Known allergic reactions to 68-Ga, or gadolinium-based contrast agents.
- 4) Treatment with another investigational drug or other intervention 2 years.
- 5) Patient has any medical, psychological or social condition that, in opinion of the investigator will make difficult for the participant to tolerate study intervention.

5.3 LIFESTYLE CONSIDERATIONS

5.3.1 Fluid and Food Intake

Subjects should follow their normal diet before and after the administration of the study drug. Subjects will be encouraged to increase fluid intake at baseline and after the image acquisition to maintain proper hydration throughout the study period and decrease radiation exposure to the urinary bladder. To enhance imaging, subjects will be encouraged to void prior to collection of study imaging post-68Ga-PSMA-11 injection.

There are no dietary or food restrictions for this trial.

5.3.2 Subject Activity Restrictions

The radioactivity administered in this study is similar to other radiopharmaceutical studies, therefore the only activity restriction is:

- Participants whom are sexually active are required to consent to use acceptable form of birth control following the imaging period (condoms for a period of seven days after injection if sexually active)

5.4 STRATEGIES FOR RECRUITMENT AND RETENTION

- Target study sample: 80 male patients, age 21 and older, diagnosed with high risk adenocarcinoma of prostate. We anticipate will need to screen 200 patients in order to reach the target enrollment. Study will enroll participants

from Houston Methodist Hospital-Department of Urology, or from external referrals by sub-investigators or other physicians. Once a possible candidate is identified, the study team will approach him over the phone/e-mail or personally during a standard of care appointment, to present information about the study. If patient expresses interest, he will be scheduled for a screening visit.

6 STUDY INTERVENTION

6.1 STUDY INTERVENTION(S) ADMINISTRATION

6.1.1 STUDY INTERVENTION DESCRIPTION

See Appendix A

Study Drug

Each milliliter of the sterile, apyrogenic drug product contains approximately 18.5-74 MBq (0.5 – 2 mCi) of active ingredient (68Ga-PSMA-11), 6 mL of sodium chloride (Sodium Chloride Injection (0.9%) without preservatives USP), and 10% of ethanol (v/v). Each dose of 68Ga-PSMA-11 solution for intravenous injection should be stored at room temperature and administered by the labeled expiration time.

6.1.2 DOSING AND ADMINISTRATION

On Day 0 of the study, the study drug dose will be 185 ± 74 MBq (5 ± 2 mCi) and will be administered by IV injection as a slow bolus and flushed with approximately 10 mL of saline solution.

A whole-body positron emission tomography/Computed Tomography (PET/CT) scan will be obtained between 60-90 minutes post-injection of study drug.

Vital signs (BP and pulse) will be taken and recorded before injection and 2 hours post injection.

All study drug administration will be done at the clinical site under the supervision of the Investigator.

Details of study drug administration will be captured in each subject's source document and transcribe onto the case report form (CRF)

6.2 PREPARATION/HANDLING/STORAGE/ACCOUNTABILITY

6.2.1 ACQUISITION AND ACCOUNTABILITY

In accordance with International Conference on Harmonisation (ICH) and US Food and Drug Administration (FDA) requirements, the Investigator and/or Drug Dispenser must at all times be able to account for all study drug.

No study agent is to be used outside of this study. Record the use of the study agent on the appropriate record. All study radiopharmaceuticals must be accounted for, whether used or unused, during the course of and at the conclusion of the study.

The Investigator is responsible for ensuring that study drugs are recorded, handled and stored safely and properly in accordance with the Code of Federal Regulations (CFR), local/state laws and used in accordance with this protocol.

68Ga-PSMA 11 will be manufactured by the Cyclotron cGMP Core Facility at Houston Methodist Research Institute.

Principal Investigator will send requisition via email for the preparation of the product. The study drug will be dispensed in a sterile 10 ml polypropylene at room temperature to be administered to the subject.

Unused product will be disposed of according to institutional regulations. Record the use and/or disposal of the study agent on the Drug Accountability record.

6.2.2 FORMULATION, APPEARANCE, PACKAGING, AND LABELING

Formulation and packaging: the finished final product 68Ga-PSMA-11 solution for intravenous administration contains 0.6 ml ethanol and 5.4 ml of sodium chloride (Sodium Chloride Injection (0.9%) without preservatives USP, in a 30 ml sterile vial.

Appearance: It is clear and colorless solution, no visible particles.

Dispensing: The product solution is aseptically dispensed into a sterile 10-mL polypropylene syringe and stored at room temperature prior to its intravenous administration to the subject.

Labeling: the label will disclose the expiration date and “For investigational use only”.

6.2.3 PRODUCT STORAGE AND STABILITY

Each dose of 68Ga-PSMA-11 solution for intravenous injection will be shipped to the PET Imaging Core and it should be stored at room temperature and administered before the labeled expiration time.

The drug product contains radioactive material and should only be handled by personnel trained in the use of radioactive isotopes with proper shielding and monitoring. Receipt and use is limited to a facility licensed by the Federal or State office of Radioactive Substances. Unused or residual waste should be disposed of as radioactive waste following the institution’s standard operating procedures (SOPs) and/or applicable regulations or guidance.

6.2.4 PREPARATION

The drug will be manufactured upon requisition from a qualified principle investigator with approved IND and IRB protocol. During drug product manufacturing, individual doses are aseptically dispensed into a sterile 10-mL polypropylene syringe and stored at room temperature prior to its intravenous administration to the patient. Each milliliter of the sterile, apyrogenic drug product contains approximately 18.5-75 MBq (0.5 – 2 mCi) of active ingredient (68Ga-PSMA-11), 0.9 mL of sodium chloride (Sodium Chloride Injection (0.9%) without preservatives USP, and 0.1 mL of ethanol.

The drug product contains radioactive material and should only be handled by personnel trained in the use of radioactive isotopes with proper shielding and monitoring. Receipt and use is limited to a facility licensed by the Federal or State office Radioactive Substances. Unused or residual waste should be disposed of a radioactive waste following the institution's standard operating procedures (SOPs) and/or applicable regulations or guidance. Each dose of 68Ga-PSMA-11 solution will be administered as a slow bolus over approximately 30 sec followed by a 10 mL saline flush.

6.3 MEASURES TO MINIMIZE BIAS: RANDOMIZATION AND BLINDING

To minimize bias, all PET/CT images will be interpreted by a board-certified radiologist. The radiologist evaluating the images will be blinded to the final outcome, such as the histopathology of any biopsies and the outcome of subsequent imaging.

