1 PROTOCOL SUMMARY

1.1 SYNOPSIS

Title:	Comparison of 68Ga-PSMA Positron Emission Tomography (PET)/CT to Conventional Imaging in Men with High Risk Prostate Cancer
Study Description:	This is a prospective, single-center, open-label pilot study of 68GA-PSMA-11 given at a single time prior to PET/CT imaging in men with localized high risk prostate cancer or biochemical recurrence. Eligible participants will undergo baseline assessments using conventional 99-Tc Bone Scan and CT of the Abdomen and Pelvis or multi-parametric MRI imaging of the prostate

Objectives:

Primary Objective

1. To evaluate the tissue distribution of 68GA-PSMA-11 PET/CT imaging in normal tissues and biopsy proven tumor and non-tumorous regions of the prostate, and also pelvic lymph nodes in high risk patients undergoing standard of care prostatectomy and bilateral lymph node dissection.
2. To determine the proportion of patients in which 68GA-PSMA-11 PET/CT altered the planned clinical management.

Secondary Objective:

1. To correlate the intensity of 68GA-PSMA-11 PET/CT uptake with respect to pathological findings.
2. To compare suspicious lesions visualized on 68GA-PSMA-11 PET /CT with standard of care diagnostic imaging modalities, additional biopsy results, or clinical follow-up performed at the discretion of the referring physician.

Endpoints:

Primary Endpoints:

1. Proportion of patients with cTxNoMo (clinically localized disease) found on final histological examination to have lymph node involvement as determined by 68GA-PSMA-11 PET/CT.
2. Proportion of patients in which 68GA-PSMA-11 PET/CT altered the planned clinical management.

Secondary Endpoints:

1. 68GA-PSMA-11 PET/CT intensity is variable, and we will evaluate what intensity endpoint is predictable of tissue involvement.
2. To compare and contrast findings in 68GA-PSMA-11 PET/CT with standard diagnostic modalities of bone scan, CTs and MRIs.

Study Population: Male patients, aged 21 or older, diagnosed with histopathological proven prostate adenocarcinoma, with no evidence of other malignancy, and Eastern Cooperative Oncology Group (ECOG) performance of 0-1.

Phase: Pilot, phase I/2

Description of Sites/Facilities
This is a single site trial that will be conducted at the Houston Methodist Hospital.

Enrolling Participants:

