Description of Study Intervention: This is a prospective, open label, single-center, single-arm, pilot diagnostic accuracy study to evaluate the tissue distribution of 68Ga-PSMA Positron Emission Tomography (PET)/CT in 80 patients with high risk localized prostate cancer or biochemical recurrence.

Subjects will receive a single IV dose of 3-7 mCi of 68Ga-PSMA (study drug) followed by PET/CT imaging 60-90 minutes after injection. All patients will be closely monitored with vital signs (blood pressure and heart rate), before and 2 hours following radiotracer administration.

Patients will receive a phone call 2 days following PET/CT to assess for adverse events.

To minimize bias, all PET/CT images will be interpreted by a board-certified radiologist. The radiologist evaluating the images will be blinded to the final outcome, such as the histopathology of any biopsies and the outcome of subsequent imaging.

Patients with study-defined high-risk features who are eligible and scheduled for radical prostatectomy or with biochemical recurrence will undergo 68Ga-PSMA-11 PET/CT injection. The results of the 68Ga-PSMA-11 PET/CT may alter patient

management in one of several ways, including the decision to not pursue surgical extirpation (e.g. in the event of extensive distant metastasis) in favor of systemic therapy. It is also possible that the extent of surgical resection may be altered, such as non-regional pelvic or retroperitoneal lymph node dissection. The alteration in planned surgical treatment from standard of care will be recorded as a secondary-end point.

Study Duration: 18 months.
Participant Duration: 6 months.

SCHEMA

Screening
Visit 1

Total:80 patients - Obtain informed consent. Screen potential participants by inclusion and exclusion criteria; obtain history, physical exam, height/weight, ECOG, safety labs

Visit 2

Administration of study intervention.
AE assessment (Phone follow-up)

Radical Prostatectomy

Systemic Therapy to be
determined attending
physician if metastatic disease
is identified

Follow up at 2 and 6 months

Visit 3 and 4

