8.5 Computed Tomography (CT) and Magnetic Resonance (MR) Imaging

A diagnostic quality MR scan (abdomen and pelvis) may be obtained (if clinically indicated) prior to surgery if not done within 6 months of the screening visit, if clinically indicated. If collected as part of screening procedures, the scan should be contrast-enhanced, unless contra-indicated for the subject. If necessary, the scan maybe obtained between the first injection of study drug and surgery.

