8.6 Bone Scan

If clinically indicated, a bone scan may be obtained prior to surgery if not done within 6 months of the screening visit. If necessary, the scan may be obtained between the first injection of study drug and surgery.

8.7 68Ga-PSMA-11 PET/CT Imaging

A whole-body positron emission tomography/Computed Tomography (PET/CT) scan will be obtained between 60-90 minutes post-injection of study drug.

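### The PET reader's blinding does not cover the baseline bone scan, CT and MRI that PET is compared with, so independence of the reads is not ensured

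*Combined protocol and SAP*

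**What the plan says.** Blinding is described three times, with one scope. Section 6.3 states that the PET radiologist "will be blinded to the final outcome, such as the histopathology of any biopsies and the outcome of subsequent imaging". Section 4.1 says "They will be blinded to the final outcome, such as the histopathology of any biopsies and the outcome of subsequent imaging", and the synopsis has "The radiologist evaluating the images will be blinded to the final outcome", followed by the same examples.

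The title announces a "Comparison of 68Ga-PSMA Positron Emission Tomography (PET)/CT to Conventional Imaging in Men with High Risk Prostate Cancer". Secondary endpoint 2 is "To compare and contrast findings in 68GA-PSMA-11 PET/CT with standard diagnostic modalities of bone scan, CTs and MRIs". Section 3 justifies that endpoint by asking, on the basis of histology, whether the modalities complement each other or whether one or more could be left out of the work-up.

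The comparator scans normally come first. According to the synopsis, "Eligible participants will undergo baseline assessments using conventional 99-Tc Bone Scan and CT of the Abdomen and Pelvis", or multiparametric MRI of the prostate. The Schedule of Activities (Section 1.2) places them at screening, and its footnote 4 accepts scans from the preceding 6 months. Two sections allow an exception: for MR, Section 8.5 says that "the scan maybe obtained between the first injection of study drug and surgery" if necessary; for the bone scan, Section 8.6 says that "the scan may be obtained between the first injection of study drug and surgery", again if necessary.

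**The concern.** A comparison of two imaging methods in the same patient is fair to both only if neither result can influence the call on the other. The blinding here protects the PET read against later information. It does not mention earlier information, and that is where the comparator usually sits.

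The exposure matters because PET positivity is a visual judgement. Sections 4.1 and 8.7.1 require focal uptake above blood pool or physiologic background, with no numeric cut-off. Section 3 itself expects equivocal readings. Those are the calls most open to influence from an enlarged node on CT or a lesion on bone scan.

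At stake is the use that Section 3 makes of secondary endpoint 2. If a conventional finding helps to turn an equivocal PET focus into a positive call, that lesion no longer counts as found by conventional imaging alone. The conventional scan can then look redundant because it contributed to the PET result. Enrolling more patients would not remove this bias.

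**Working it through.** The protocol states no figure that depends on this point, and Section 9.1 says that the sample size was not statistically determined, so there is nothing to reproduce. The check is mainly one of text.

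1. **Scope of blinding.** The synopsis, Section 4.1 and Section 6.3 all name the final outcome, with biopsy histopathology and subsequent imaging as examples. None mentions imaging done before PET.
2. **Where the comparator falls.** The conventional scans are baseline assessments at or before screening. They are neither final outcome nor subsequent imaging. Footnote 1 of Section 1.2 includes prior radiographic exams in the medical history review, so the results are in the study record before the PET read.
3. **Other safeguards.** No section says who reads the conventional scans, whether that person may also read the PET/CT, or in what order the reads are recorded. Section 9 adds nothing on reading.
4. **Scans after injection.** These count as subsequent imaging, so the PET reader is masked to them. Nothing masks their readers to the PET result.

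The arithmetic below is an illustration only. Its inputs are:

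- *c*, CT/MRI sensitivity for nodal metastasis: 0.30-0.80 (Section 2.1).
- *s*, stand-alone PET sensitivity: 0.60-0.80 (assumed).
- *f*, share of PET-missed, conventional-positive lesions that the PET reader upgrades: 0.25-0.50 (assumed).
- The two tests are assumed conditionally independent given disease.

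Apparent PET sensitivity = s + f(1 − s)c, so the rise is f(1 − s)c. Lesions found by conventional imaging only = (1 − f)(1 − s)c.

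| s | c | f | Rise in PET sensitivity | PET minus conventional, points | Conventional-only per 100 lesions |
|---|---|---|---|---|---|
| 0.80 | 0.30 | 0.25 | 0.25 × 0.20 × 0.30 = 0.015 | +50.0 → +51.5 | 6.0 → 4.5 |
| 0.70 | 0.50 | 0.50 | 0.50 × 0.30 × 0.50 = 0.075 | +20.0 → +27.5 | 15.0 → 7.5 |
| 0.70 | 0.80 | 0.50 | 0.50 × 0.30 × 0.80 = 0.12 | −10 → +2 | 24 → 12 |
| 0.60 | 0.80 | 0.50 | 0.50 × 0.40 × 0.80 = 0.16 | −20 → −4 | 32 → 16 |

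The first and last rows are the extremes of the assumed ranges: 1.5 and 16 points. In the third row the sign of the difference changes. Whatever s and c are, the conventional-only count falls by the fraction f, and that count bears most directly on whether a modality could be dropped.

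**The case against.** The strongest reply is that the protocol is silent; it does not say that the reader will see prior imaging. A reader might infer that the two sets of reads are in fact not independent. The documents do not support that: the examples of what is masked are introduced as examples, not as a complete list, and site practice may already separate the reads. What stands is that independence is not ensured.

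A reader might also infer that the reads borrow from each other in both directions. For any one scan the exposure runs one way. A baseline scan reported before PET cannot borrow from it, and a scan made after injection is masked from the PET reader. The second route is also narrow: such scans need a clinical indication, no scan within 6 months, and necessity. Despite its heading, the text of Section 8.5 names MR only.

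The positivity rule gives some protection, since a node seen on CT without focal uptake above blood pool cannot be called positive. That limits the upgrade rate but does not settle equivocal foci. The illustration should also not be carried over to primary endpoint 1. That endpoint concerns patients with clinically node-negative disease; if node-negative means negative on conventional imaging, there are few or no conventional-positive nodes to upgrade.

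Finally, this is a secondary, descriptive endpoint in an exploratory pilot. Section 3 ties it to histology, and Section 8.9 makes tumor foci on H&E sections the gold standard for imaging comparison. An informed read may be the right one for the management-change endpoint. All of this is fair and limits the weight of the point. Histology as reference does not remove the problem, however, because the PET call being checked against it may already contain the conventional result.

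**Conclusion.** The point holds as a gap in the stated bias safeguard. The blinding omits the baseline comparator, nothing else in the protocol fills the gap, and the plan as written permits a visual PET call to be made with knowledge of the scan it is compared with. Separately, the few MR or bone scans made after injection may be read with knowledge of the PET result.

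It affects secondary endpoint 2 and the accuracy analyses. The management-change endpoint does not need a masked read. The direction of the risk is towards a flattering view of PET and too few conventional-only findings. The size is unknown. The range of about 1.5 to 16 points is hypothetical: only the 30-80% CT/MRI sensitivity comes from the protocol, and the rest (PET sensitivity 60-80%, upgrading of 25-50%, conditional independence) is assumed. It should not be quoted as an estimate of bias in this trial.

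**What to change.** In Section 6.3, and to match in the synopsis and Section 4.1, state the following.

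- **First read.** The PET/CT is read without conventional images or reports. Where existing staffing allows, the reader is a radiologist who did not report that patient's conventional scans; otherwise the case is flagged. This condition is needed because withholding the images does not mask someone who has already reported them. The region and node calls of Section 8.7.1 are locked on the CRF with a time stamp.
- **Second read.** The same radiologist then makes the integrated read with all imaging. This is the read used for care and for the management-change endpoint.
- **Analysis.** The locked read is used for secondary endpoint 2 and the accuracy analyses. The main comparison uses conventional reports finalised before the PET result is released. Later reports are flagged and added in a sensitivity analysis.

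The cost is a short extra reading step and a time-stamped CRF entry for calls that are already recorded by region and node station. No extra scan or patient is needed, and no additional reader has to be engaged. The downside is that some comparator scans made after PET leave the main comparison. Because those scans were clinically indicated, their number and the reason for each should be reported, so that any selection is visible.
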